## 16. Secondary Analyses

Subscale scores will be analyzed analogously to the primary endpoint. Exploratory analyses may assess associations between bonding outcomes and selected caregiving behaviors or demographic variables using correlation and regression models, with model assumptions checked and documented.

## 17. Covariates and Sensitivity Analyses

Potential covariates (e.g., education level, partner's employment, caregiving involvement) may be considered in adjusted models. Sensitivity analyses may exclude participants with major deviations or missing key assessments.

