## 1. Synopsis

- Design: Interventional, randomized, parallel-group, three-arm study conducted in maternity units.
- Arms: (A) Early one-time skin-to-skin contact; (B) Frequent skin-to-skin contact; (C) Standard care comparator.
- Primary Endpoint: Paternal-Infant Attachment Scale (PIAS) total score at approximately 3 months postpartum (points; higher scores indicate stronger bonding).
- Secondary Endpoints: PIAS subscale scores; frequency (days/week) and daily minutes of skin-to-skin contact; selected caregiving behaviors.
- Population: Adult fathers of healthy term singleton newborns.
- Setting: University and state hospital obstetrics units in Türkiye.
- Duration per participant: Baseline assessment soon after birth and a follow-up assessment around 3 months postpartum.

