## 3. Objectives

Primary Objective. To determine whether father-infant skin-to-skin contact improves paternal-infant bonding compared with standard care.

Secondary Objectives. To compare subscale scores of bonding, describe skin-to-skin frequency and duration, and explore associations with selected caregiving behaviors and sociodemographic factors.

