## 4. Endpoints

Primary Endpoint. PIAS total score at 3 months postpartum.

Secondary Endpoints. PIAS subscale scores; frequency of skin-to-skin (days/week); daily minutes of skin-to-skin; indicators of paternal involvement.

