## 7. Eligibility Criteria

### Inclusion Criteria:

- Fathers aged 18 years or older.
- First-time fathers residing with the mother and infant.
- Able to provide skin-to-skin contact (e.g., sessions of approximately 15 minutes) within a defined post-birth window.
- At least primary school education.
- Infant: healthy, term ( $\approx$ 38-42 weeks' gestation), singleton, with birth weight within an acceptable range per protocol.

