## 9. Assessments and Schedule

Assessments include a baseline questionnaire administered soon after birth and a follow-up evaluation at approximately 3 months postpartum, which includes the PIAS. Additional questionnaires capture frequency (days/week) and daily minutes of skin-to-skin, and caregiving behaviors. All assessments are performed with standardized instructions.

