## 15. Primary Endpoint Analysis

Group comparisons of PIAS total scores at 3 months postpartum will be performed using a nonparametric omnibus test (e.g., Kruskal-Wallis). If the omnibus test is significant, post-hoc pairwise comparisons will be conducted with appropriate adjustments for multiplicity.

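### Section 17 names caregiving involvement as a covariate although paternal involvement is a secondary endpoint; an arm comparison adjusted for it may not estimate the total effect of assignment

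*Combined protocol and SAP*

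**What the plan says.** SAP Section 17 lists potential covariates by example. After education level and partner's employment comes "caregiving involvement) may be considered in adjusted models". The section does not say whether these models contain an arm term or what they are meant to estimate.

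Elsewhere the same or a closely related construct is an outcome. The secondary endpoints in the Synopsis include "daily minutes of skin-to-skin contact; selected caregiving behaviors"; those in Section 4 include "daily minutes of skin-to-skin; indicators of paternal involvement".

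On timing, Section 9 describes "a baseline questionnaire administered soon after birth" and a follow-up at about 3 months, then adds: "Additional questionnaires capture frequency (days/week) and daily minutes of skin-to-skin, and caregiving behaviors". It does not tie the caregiving items to a visit. Section 7 limits enrolment to "First-time fathers residing with the mother and infant".

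The primary analysis in Section 15 is a "nonparametric omnibus test (e.g., Kruskal-Wallis" being the example) with no covariates stated, and Section 16 treats the subscales in the same way. Section 16 also allows exploratory correlation and regression of bonding on caregiving behaviors or demographic variables. This matches the secondary objective in Section 3, which is to "explore associations with selected caregiving behaviors and sociodemographic factors".

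**The concern.** A variable that the plan treats as a possible result of assignment is also offered as something to adjust for. The primary objective asks whether skin-to-skin contact improves bonding compared with standard care, which is most naturally the total effect of being assigned to a schedule. If that effect runs partly through greater paternal involvement, holding involvement fixed removes that part. If involvement and bonding also share causes, such as a father's motivation, the adjusted coefficient need not equal even the direct effect.

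The adjusted and unadjusted arm differences would then answer different questions. A gap between them would not by itself show that the main result is fragile, nor would agreement show that it is robust. A reader who compared the covariate list with Section 4 could work this out, but the plan does not say it.

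**Working it through.** The plan gives no sample size, SD or effect size, so it has no figure of its own to reproduce. The check compares the sections first and then works out the size of the shift under assumed values.

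**1. Is involvement an outcome?** The Synopsis and Section 4 list it as one. The three terms used (caregiving involvement, caregiving behaviors, indicators of paternal involvement) are undefined, so it is an inference that they share a measure.

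**2. Is it measured after randomisation?** Very probably. A first-time father has no earlier child with whom involvement could have been recorded, and little care of this infant can precede the schedule. This is not certain: the plan states neither the time of randomisation nor the visit at which caregiving is asked about.

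**3. Could an adjusted model compare arms?** Nothing rules it out. Section 16 already covers regressions of bonding on caregiving behaviors. Section 17 is a separate covariate section that sets involvement beside two conventional adjustment variables. No section limits covariates to variables fixed before randomisation.

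**4. Size of the shift.** Take least squares of PIAS (Y) on arm and involvement (M), with a common slope:

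- adjusted difference = unadjusted difference - slope x (arm difference in M)
- slope = rho x SD_Y / SD_M, within arm
- dividing by SD_Y, with d = (arm difference in M) / SD_M: **unadjusted - adjusted = rho x d**

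The documents give neither rho nor d. Over an assumed range, in within-arm outcome SDs:

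| d | rho = 0.1 | rho = 0.3 | rho = 0.5 |
|---|---|---|---|
| 0 | 0 | 0 | 0 |
| 0.2 | 0.02 | 0.06 | 0.10 |
| 0.5 | 0.05 | 0.15 | 0.25 |
| -0.2 | -0.02 | -0.06 | -0.10 |
| -0.5 | -0.05 | -0.15 | -0.25 |

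Where the shift is negative, the adjusted difference exceeds the unadjusted one. A three-arm simulation with 200,000 per arm agreed with every cell to within 0.004. That confirms the algebra and says nothing about this trial.

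**5. Shared causes.** In a second, two-arm illustration, scaled so that involvement has within-arm SD 1 and the independent error in PIAS has SD 1, assume a direct effect of 0.30, an arm effect on involvement of 0.5 and a slope of PIAS on involvement of 0.3. The total effect is 0.30 + 0.5 x 0.3 = 0.45.

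- No common cause: the unadjusted estimate is 0.453 and the adjusted one 0.301, so adjustment returns the direct effect.
- A common cause loading 0.4 on both: the within-arm slope is 0.3 + 0.4 x 0.4 = 0.46, so the expected adjusted value is 0.45 - 0.46 x 0.5 = 0.22. The simulation gave 0.447 unadjusted and 0.216 adjusted, which is below the direct effect.
- If the arms do not change involvement, both estimates stay at about 0.30.

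**The case against.** The strongest reply is that the plan contains no adjusted arm comparison. Arms are compared only in Sections 15 and 16, by rank tests without covariates. The only regressions specified are the exploratory association models in Section 16, and the examples in Section 17 fall into the same two classes, demographic and caregiving. Read that way, Section 17 serves the association objective and distorts no treatment effect. The sensitivity analyses it describes exclude participants with deviations or missing assessments; adjusted models are not given that role. Harm also needs a chain of conditions: the model is run, it has an arm term, involvement is chosen from a list of examples, it is measured after randomisation, and assignment changes it. The magnitudes rest on assumed inputs.

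Much of this stands. The association reading is reasonable, the chain is real, and the size in this trial is unknown. These points limit the importance of the issue but do not remove it. Section 16 already provides the association models, so a separate section on covariates and adjusted models naturally extends to arm comparisons. The plan also goes beyond leaving the list open: it names a specific variable that is poorly suited to that use.

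It can also be said that deleting the term would remove a legitimate regressor from association models. It would not, because Section 16 already allows caregiving behaviors there.

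**Conclusion.** The concern holds, as a minor point with medium confidence. Section 17 permits an arm comparison adjusted for a variable that is probably both post-randomisation and an outcome, and such a model may not estimate the total effect of assignment. The confirmatory result is not at risk, because the primary omnibus test and the subscale tests state no covariates.

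The size and direction in this trial cannot be derived from the documents. The assumed range of -0.25 to 0.25 outcome SD includes zero and depends on a linear model with a common slope. The conclusion also rests on two inferences: that caregiving involvement is the same as, or close to, the endpoint measure, and that it is recorded after randomisation.

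**What to change.** Three small edits to the SAP:

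1. Remove caregiving involvement from the covariate examples in Section 17.
2. State there that covariates in any model comparing arms are limited to variables fixed before randomisation, such as education level and partner's employment as recorded at baseline.
3. Keep involvement as an outcome, or use it in a Section 16 exploratory model labelled as association or mediation and not reported as an adjusted treatment effect.

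The cost is two or three sentences. No data collection or participant burden is added and no planned analysis is lost. If the sponsor meant only association models, the edits make that explicit.

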## 5. Trial Design

Randomized, parallel assignment with three arms and approximately equal allocation. The early one-time arm includes a single skin-to-skin session soon after birth. The frequent arm includes repeated sessions (e.g., at least 15 minutes per session on most days). The comparator arm receives routine postnatal care without a structured schedule.

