# Statistical Analysis Plan (SAP)

This SAP outlines analyses for the primary and secondary endpoints, populations for analysis, handling of missing data, and statistical thresholds. Analyses use a two-sided alpha of 0.05 unless otherwise noted.

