## 13. Analysis Populations

Intent-to-Treat (ITT): All randomized participants with at least one post-baseline assessment. Per-Protocol (PP): Subset without major protocol deviations.

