## 18. Missing Data Handling

Extent and patterns of missing data will be summarized. Analyses will primarily use available cases; if necessary, sensitivity analyses such as multiple imputation may be considered consistent with the nonparametric framework.

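### Excluding fathers with missing key assessments (Section 17) cannot test robustness to missing 3-month PIAS scores, and the plan commits to no analysis that can

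*Combined protocol and SAP*

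**What the plan says.** The primary endpoint (Section 4) is the "PIAS total score at 3 months postpartum". Section 9 schedules "a baseline questionnaire administered soon after birth and a follow-up evaluation at approximately 3 months postpartum, which includes the PIAS". It adds: "Additional questionnaires capture frequency (days/week) and daily minutes of skin-to-skin, and caregiving behaviors", without saying when these are completed. No other follow-up visit is described.

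Section 15 compares the arms with a nonparametric omnibus test, Kruskal-Wallis being the example. Pairwise tests follow only if it is significant. It names no analysis set. On missing data, Section 18 states: "Analyses will primarily use available cases". The same sentence goes on to allow multiple imputation as a sensitivity analysis if it is judged necessary.

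Section 13 defines an ITT set, limited to randomised fathers with some assessment after baseline, and a second set: "Per-Protocol (PP): Subset without major protocol deviations". No section assigns an analysis to that second set. Section 17 then says: "Sensitivity analyses may exclude participants with major deviations or missing key assessments". *Key assessments* is not defined anywhere.

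**The concern.** A sensitivity analysis for missing outcomes should change the assumption made about the fathers whose outcome is unknown. The missing-assessment exclusion does not. It either reproduces the primary result or trims the same set of returning fathers further.

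The risk is false reassurance. Fathers who bond less may be less likely to return, and the frequent arm alone carries a repeated schedule that could affect who stays. If loss of that kind differs between arms, the available-case comparison is biased. Heavier loss from a skin-to-skin arm would flatter that arm, and heavier loss from standard care would hide a benefit. The Section 17 exclusion would show neither, yet its agreement with the primary result could be reported as robustness.

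**Working it through.** The documents give no sample size, SD, attrition rate or deviation rate, so there is no figure of the plan's own to reproduce. The check is first a comparison of analysis sets, then arithmetic on assumed values.

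**Step 1: the sets.** Let R be all randomised fathers, A those with a 3-month PIAS total, Q those with the other questionnaires complete, and D those with a major deviation.

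| Analysis | Fathers analysed | Relation to the primary |
|---|---|---|
| Primary, available cases (Sections 15 and 18) | A | – |
| Exclude missing key assessments, meaning the PIAS (Section 17) | R without (R without A) = A | Identical: same statistic, same p-value |
| Exclude missing key assessments, read more widely (Section 17) | A and Q | Subset of A |
| Exclude major deviators (Sections 13 and 17) | A without D | Differs if any father in A deviated |

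No row brings in a father outside A. The ITT definition does not bring them in either: it requires an assessment after baseline, and the one scheduled follow-up is the visit that yields the PIAS.

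**Step 2: what would go unseen.** Let lost fathers in every arm score delta SD lower than returning fathers in the same arm, and let the fraction lost be L. The arm's true mean is (1 − L) × m + L × (m − delta) = m − L × delta, where m is the mean of those who returned. The observed mean is therefore too high by L × delta, and the difference between two arms is biased by

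bias = delta × (L₁ − L₂).

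All inputs below are assumptions.

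| Loss in the two arms | Difference | delta = 0.5 SD | delta = 1.0 SD |
|---|---|---|---|
| 20% vs 10% | 0.10 | 0.05 SD | 0.10 SD |
| 25% vs 10% | 0.15 | 0.075 SD | 0.15 SD |
| 40% vs 20% | 0.20 | 0.10 SD | 0.20 SD |

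**Step 3: illustrative simulation.** 2000 trials were simulated with 50 fathers per arm, no true effect and a Kruskal-Wallis test. The PIAS was missing in about 27% of the frequent arm, with low scorers lost more often, and in 15% of each other arm at random. Major deviations occurred in about 30% of the frequent arm, again related to score, and in 5% of each other arm. Another questionnaire was missing at random in 8%. All of these inputs are assumed.

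- Excluding missing PIAS: p-value identical to the primary in 2000 of 2000 trials.
- Also excluding fathers with the other questionnaire missing: p-value different in every trial, but the set is still a subset of A.
- Excluding deviators: p-value different in every trial; the conclusion at 0.05 changed in 23%.
- Rejection with no true effect: 4.6% with full data, 24.8% with available cases, 45.6% after also excluding deviators.

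By Step 1, the PIAS exclusion would reproduce the 24.8% exactly. The rates depend wholly on the assumed inputs; the identity does not.

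**The case against.** Four points can be made for the plan.

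1. **The deviator exclusion is informative.** A reader might infer that both Section 17 analyses repeat something already planned and that neither can test robustness. The documents do not support that. Section 13 only defines the per-protocol set and no section assigns an analysis to it, so Section 17 appears to be its only use. The result can differ from the primary, as the simulation shows. This point stands in full, with two limits: the set is selected after randomisation and can be more biased than the primary, and it says nothing about missing outcomes.

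2. **Key assessments may mean more than the PIAS.** The term is plural, Section 9 lists several questionnaires, and the sentence follows one on covariate-adjusted models. Exact identity with the primary therefore holds only on the narrow reading. This stands, but the wider reading still deletes fathers without varying the assumption about those lost.

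3. **Section 18 allows multiple imputation.** A reader might infer that the plan has no missing-data sensitivity analysis at all. That is too strong, since one is named. It is doubly conditional, however, and has no model, variables or trigger. In its usual form it assumes missing at random, and Section 9 places the PIAS only at follow-up, so no baseline score is described to inform it. It would not by itself examine lower bonding among lost fathers.

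4. **The size is attrition bias, not harm done by Section 17.** The bias would exist without that sentence, it is expressed as a mean difference while the primary is a rank test, and it assumes equal deltas across arms. This is fair. The figures show what the check would fail to reveal.

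**Conclusion.** The concern holds for the missing-assessment exclusion. Read as the PIAS, its difference from the available-case primary is exactly zero; read more widely, it is a smaller complete-case analysis with the same assumption about fathers who did not return. Excluding deviators is a legitimate but separate question. The one analysis that addresses missing data is optional and unspecified.

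The undetected bias in an arm difference is 0.05 to 0.20 SD, given assumed deltas of 0.5 to 1.0 SD, equal across arms, and assumed differences in loss of 10 to 20 percentage points. If loss is equal across arms and delta is the same in each, this bias is zero. The documents do not show that selective loss will occur, only that the plan commits to no analysis that would reveal it. The primary test can still be run as written, so this is a change the SAP should make rather than a fatal fault.

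**What to change.** **Section 17.** Delete the exclusion for missing assessments. State that excluding major deviators is the per-protocol analysis of the primary endpoint.

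**Section 18.** Replace the optional imputation with a planned one, for example:

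> For all randomised fathers, including those outside the ITT definition in Section 13, missing 3-month PIAS totals will be multiply imputed from arm and baseline variables. Imputed scores will then be lowered by 0, 0.25, 0.5 and 1.0 SD, in all arms together and in each arm alone, including standard care. For each shift, the omnibus test and each comparison of a skin-to-skin arm with standard care will be repeated and pooled by a rule stated in advance. The smallest shift that changes the omnibus conclusion will be reported and, where pairwise tests are reached, the smallest shift that changes each pairwise conclusion.

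The zero shift is the missing-at-random analysis. Shifting standard care alone covers the case where loss from that arm hid a benefit. The imputation variables and the pooling rule for the rank tests need to be written in before outcomes are seen. The shift sizes are a proposal and can be changed with a reason.

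**Cost.** SAP wording and a few hours of programming, with no new data. The downside is that reported robustness may look weaker.

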## 18. Missing Data Handling

Extent and patterns of missing data will be summarized. Analyses will primarily use available cases; if necessary, sensitivity analyses such as multiple imputation may be considered consistent with the nonparametric framework.

## 19. Multiplicity and Software

Multiplicity adjustments will be applied to control type I error for multiple pairwise tests when applicable. Analyses will be performed using standard statistical software (e.g., SPSS, R, or Python).

## 20. Administrative Information

Sponsor/Institution: Çanakkale Onsekiz Mart University (ÇOMÜ). Study officials and investigators are listed in the trial record. This document is intended for public posting on ClinicalTrials.gov and does not include participant names or other personally identifiable information.

Any deviations from this plan will be documented in the results section when outcomes are reported.
